Appendix 4:	Breakthrough Designation Status: Melanoma	104
Appendix 5:	Clinical Studies of Bempegaldesleukin (NKTR-214)	105

ABBREVIATIONS

Abbreviation or Term	Definition
ACE	angiotensin converting enzyme
ADA	anti-drug-antibodies
AE	adverse event
AESI	adverse event of special interest
ALC	absolute lymphocyte count
ALT (SGPT)	alanine transaminase (serum glutamic pyruvic transaminase)
ANC	absolute neutrophil count
ARDS	acute respiratory distress syndrome
AST (SGOT)	aspartate transaminase (serum glutamic oxaloacetic transaminase)
AUC	area under the concentration-time curve
Bempeg, BEMPEG	abbreviation for bempegaldesleukin, the International Nonproprietary Name (INN) for NKTR-214
Bempegaldesleukin	International Nonproprietary Name (INN) for NKTR-214
bpm	beats per minute
CDC	Centers for Disease Control and Prevention
CFR	Code of Federal Regulations
CI	confidence interval
C _{max}	maximum concentration
COVID-19	coronavirus disease 2019, caused by the severe acute respiratory syndrome coronavirus 2 (SARS-CoV-2)
CRC	Cohort Review Committee
CRF	case report form
CRS	cytokine release syndrome
CTCAE	Common Terminology Criteria for Adverse Events
CVA	cerebrovascular accident
DCI	data collection instrument
DILI	drug-induced liver injury
DLT	dose-limiting toxicity
DVT	deep vein thrombosis
ECG	electrocardiogram
ECLA	electrochemiluminescence assay
eCOA	electronic clinical outcomes assessments

Abbreviation or Term	Definition
ECMO	extracorporeal membrane oxygenation
eCRF	electronic case report form
EDC	electronic data capture
eGFR	estimated glomerular filtration rate
EOI	end of infusion
FDA	Food and Drug Administration
FiO ₂	fraction of inspired oxygen
FSH	follicle-stimulating hormone
GCP	Good Clinical Practice
GM-CSF	granulocyte-macrophage colony-stimulating factor
HBsAg	hepatitis B surface antigen
HBV	hepatitis B virus
HCG	human chorionic gonadotropin
HCV	hepatitis C virus
HIV	human immunodeficiency virus
HLA	human leukocyte antigen
ICF	informed consent form
ICH	International Council for Harmonisation
IEC	independent ethics committee
IFN	interferon
IL-2, IL-3, IL-4, IL-5, IL-6, IL-7, IL-8, IL-10, IL-18	interleukin-2, interleukin-3, interleukin-4, interleukin-5, interleukin-6, interleukin-7, interleukin-8, interleukin-10, interleukin-18
IND	Investigational New Drug application
IRB	institutional review board
IRT	Interactive Response Technology
IV	intravenous
kg	kilogram
LDH	lactate dehydrogenase
LLOQ	lower limit of quantitation
МСР	monocyte chemotactic protein
MDRD	Modification of Diet Renal Disease
MedDRA	Medical Dictionary for Regulatory Activities

Abbreviation or Term	Definition	
MERS-CoV	Middle East respiratory syndrome coronavirus	
mg	milligram	
min	minute(s)	
MIP	macrophage inflammatory protein	
mL	milliliter	
mm Hg	millimeters of mercury	
MMWR	Morbidity and Mortality Weekly Report	
msec	millisecond	
MTD	maximum tolerated dose	
NaCl	sodium chloride	
NCI	National Cancer Institute	
NK	natural killer	
NKTR-214	bempegaldesleukin (International Nonproprietary Name)	
NOAEL	no observed adverse effect level	
NSAIDs	nonsteroidal anti-inflammatory drugs	
NSCLC	non-small cell lung cancer	
NYHA	New York Heart Association	
OTC	over-the-counter	
PaO ₂	partial pressure of arterial oxygen	
PaO ₂ /FiO ₂	ratio of the partial pressure of arterial oxygen to the fraction of inspired oxygen	
PARP	polyadenosine diphosphate ribose polymerase	
РВМС	peripheral blood mononuclear cell	
PD-L1	programmed cell death ligand 1	
PE	pulmonary embolism	
PEG	polyethylene glycol	
РК	pharmacokinetic	
q3w	every 3 weeks	
QTc	corrected QT interval	
QTcF	QT interval corrected using Fridericia's formula	
R	randomization	
RCC	renal cell carcinoma	
RECIST	Response Evaluation Criteria in Solid Tumors	

Abbreviation or Term	Definition	
rhIL-2	recombinant human interleukin-2	
RT-PCR	reverse transcription polymerase chain reaction	
RP2D	recommended Phase 2 dose	
SAE	serious adverse event	
SAP	statistical analysis plan	
SARS	severe acute respiratory syndrome	
SARS-CoV-2	severe acute respiratory syndrome coronavirus 2, the virus causing COVID-19	
SIRS	systemic inflammatory response syndrome	
SOC	standard of care	
SOP	standard operating procedure	
SpO ₂	oxygen saturation	
SUSAR	suspected unexpected serious adverse reaction	
TEAE	treatment-emergent adverse event	
TIA	transient ischemic attack	
T _{max}	time to maximum concentration	
TNF	tumor necrosis factor	
Treg	regulatory T cell	
ULN	upper limit of normal	
US, USA	United States of America	
WFI	Water for Injection	
WHO	World Health Organization	
WOCBP	Women of childbearing potential	

1.0 STUDY SYNOPSIS

Title of Study:	A Multicenter, Phase 1b, Randomized, Double-Blind, Placebo-Controlled Trial of the Safety, Tolerability, Pharmacokinetics, and Pharmacodynamics of a Single Dose of Bempegaldesleukin (NKTR-214) Plus Standard of Care versus Placebo Plus Standard of Care in Adults with Mild COVID-19				
Sponsor:	Nektar Therapeutics				
Name of Finished Product(s):	Bempegaldesleu	Bempegaldesleukin (NKTR-214 drug product)			
Name of Active Ingredient (s):	Bempegaldesleu	ukin (NKTR-214) drug substance			
Phase of Development:	Phase 1b				
Objectives:	 To evaluate bempegald bempegald this docume 2019; SAR To evaluate intravenous bempegald To assess th absolute lyn Secondary obje To estimate To evaluate To evaluate To determin To evaluate 	bempegaldesleukin plus standard of care (referred to in this document as bempegaldesleukin/SOC) compared with placebo plus standard of care (referred to in this document as placebo/SOC) in patients with mild COVID-19 (coronavirus diseas 2019; SARS-CoV-2). To evaluate the safety and tolerability of bempegaldesleukin administered as a single intravenous (IV) dose and to define the recommended Phase 2 dose (RP2D) of bempegaldesleukin in patients with mild COVID-19. To assess the effect of bempegaldesleukin on the time course and extent of changes i absolute lymphocyte counts. econdary objectives: The secondary objectives listed below involve comparison of bempegaldesleukin/SOC ersus placebo/SOC in patients with mild COVID-19: To estimate the incidence of adverse events (AEs).			
1	Patient state	meaning/interpretation. The scale is as follows: Descriptor	Score		
	Uninfected	Uninfected; no viral RNA detected	0		
	Ambulatory	Asymptomatic; viral RNA detected	1		
	mild disease	Symptomatic; independent	2		
		Symptomatic; assistance needed	3		
	Hospitalized:	Hospitalized, no oxygen therapy ^a	4		
	Moderate disease	Hospitalized; oxygen by mask or nasal prongs	5		
	Hospitalized:	Hospitalized; oxygen by non-invasive ventilation or high-flow	6		
	Severe disease	Intubation and mechanical ventilation, $PaO_2/FiO_2 \ge 150$ or $SpO_2/FiO_2 \ge 200$	7		
		Mechanical ventilation, PaO ₂ /FiO ₂ < 150 (SpO ₂ /FiO ₂ < 200) or vasopressors Mechanical ventilation, PaO ₂ /FiO ₂ < 150 and vasopressors, dialysis,	8 9		
		or ECMO	10		

	Eligible patients will be enrolled into 1 of 3 dose cohorts with doses ranging from 0.00075 mg/kg to 0.003 mg/kg. The first two patients randomized and treated in each dose cohort (1 with bempegaldesleukin/SOC and 1 with placebo/SOC) will serve as sentinel patients. Enrollment in each cohort will be staggered as follows. A Cohort Review Committee (CRC) will monitor blinded safety and tolerability data for the first 72 hours after study drug administration from the 2 sentinel patients before additional patients in that cohort are treated. If the CRC determines additional patients may be randomized, 2 patients will be randomized (1 with bempegaldesleukin/SOC and 1 with placebo/SOC), treated with study drug, and observed for 72 hours. For every 2 patients, the Medical Monitor will review the blinded safety and tolerability data for the first 72 hours after study drug administration to determine if the next 2 patients may be randomized. If it is not possible to assess the protocol-defined DLT criteria (see Section 5.3.2.1.1), the Medical Monitor will request a review of the safety data by the CRC. After 10 patients have completed a 7-day observation period for dose-limiting toxicity (DLT; see Section 5.3.2.1 for additional details), the CRC will assess the accumulated, blinded safety and tolerability data, as well as any available pharmacokinetic, pharmacodynamic, and disease measurement data, to determine whether dose escalation or de-escalation from the tested bempegaldesleukin dose level is warranted. This decision will be based on blinded data using pre-defined criteria, including the proportion of patients who experience a DLT (see Section 5.3.1). Patients who drop out of the study for reasons other than a DLT, before the DLT evaluation period (Days 1 to 7) has elapsed, may be replaced.			

Key Eligibility Criteria:	The following list contains key eligibility criteria only; a full list of eligibility criteria is provided in Section 4.0.
	 Key Inclusion Criteria: Provide written, informed consent to participate in the study and follow the study procedures.
	 Male or female patients, age 18 years or older on the day of signing the informed consent form.
	• Agrees to admission to an in-patient facility for monitoring from Days 1 to 8, inclusiv
	• Symptoms of mild illness with COVID-19 (eg, fever, cough, sore throat, malaise, headache, muscle pain, gastrointestinal symptoms) without shortness of breath, dyspnea, or clinical signs indicative of more serious COVID-19.
	• Confirmed COVID-19 determined by a positive, documented SARS-CoV-2 infection determined by a commercial or public health assay in any specimen within 4 days priot to the screening visit or during the 7-day screening period.
	• Respiratory rate < 20 breaths per minute, heart rate < 90 beats per minute (bpm).
	• Oxygen saturation by pulse oximetry > 93% on room air.
	• Body mass index $< 35 \text{ kg/m}^2$.
	• Estimated glomerular filtration rate (eGFR) \geq 30 mL/min.
	• Alanine transaminase (ALT) or aspartate transaminase (AST) < 2 × upper limit of normal (ULN) and total bilirubin < 1.5 × ULN.
	• Agrees to not participate in another clinical trial for the treatment of COVID-19 while on study unless the patient's condition has worsened and is considered to be moderate severe, or critical by the Investigator.
	Key Exclusion Criteria:
	• Shortness of breath, hypoxia (ie, the ratio of the partial pressure of arterial oxygen to the fraction of inspired oxygen [PaO ₂ /FiO ₂] ≤ 300 mm Hg), or signs of serious lower airway disease.
	• C-reactive protein, lactate dehydrogenase (LDH), or interleukin-6 (IL-6) > 1.5 × ULN
	• D-dimer or ferritin $> 1.5 \times ULN$.
	• Imminently requiring, or currently on, mechanical ventilation or extracorporeal membrane oxygenation (ECMO).
	• Systolic blood pressure < 90 mm Hg or diastolic blood pressure < 60 mm Hg.
	• Evidence of acute respiratory distress syndrome (ARDS) or systemic inflammatory response syndrome (SIRS)/shock.
	• Known cardiovascular history, including unstable or deteriorating cardiac disease.
	• Autoimmune disease.
	• History of pulmonary embolism (PE), deep vein thrombosis (DVT), or prior clinically significant venous or non-cerebrovascular accident/transient ischemic attack arterial thromboembolic event.
	• Central nervous system disease or evidence of central nervous system dysfunction.
	History of pulmonary disease, including cystic fibrosis.
	• Requirement for > 2 anti-hypertensive medications.
	• Unwilling to refrain from alcohol consumption from Day 1 of admission to the in-patient facility until discharge from the facility.
	• Adrenal insufficiency.

Product Dose and	Test Product: The starting dose of bempegaldesleukin will be 0.00075 mg/kg IV.
Mode of Administration for:	Comparator Product : Placebo control will consist of sterile normal saline solution administered at the same volume as the active administration.
	Standard of Care : All patients will receive the standard of care for COVID-19 determined by the Investigator or institution, which should follow the approved prescribing guidelines in their country and institution.
Pharmacodynamics and Biomarkers:	Blood samples for analyses of absolute lymphocyte counts, DNA/RNA sequencing, SARS-CoV-2 serology, immune cell profiling, including profiling of SARS-CoV-2 specific T cells, and cytokines will be collected. Detection of SARS-CoV-2 nucleic acid in respiratory specimens will be measured using oropharyngeal swabs and anterior nares or nasopharyngeal swabs collected in a manner consistent with the Centers for Disease and Control (CDC) specimen collection guidelines (CDC 2020b). Samples will be collected at various scheduled sample times from predose to the 30-day follow-up visit (see Section 1.2).
Pharmacokinetic and Immunogenicity Evaluation:	Blood samples for pharmacokinetic and immunogenicity will be collected from patients at multiple scheduled sampling times during the study. Validated methods will be used to measure plasma concentrations of bempegaldesleukin. Pharmacokinetic parameters such as maximum concentration (C_{max}), time to C_{max} (T_{max}), and area under the concentration-time curve (AUC) will be estimated from plasma concentration-time data where possible. Validated methods will be used to measure anti-drug antibodies and their ability to neutralize bempegaldesleukin.
Safety Evaluation:	Assessment of safety will be determined by an ongoing review of the following:
	• AEs, including treatment-emergent AEs, incidence of treatment-related AEs, SAEs, and death.
	• The AE of special interest, cytokine release syndrome (CRS).
	Clinical laboratory tests (blood and urine sampling).
	• Vital signs.
	Physical examination.
Disease	The disease measurements are:
Measurement:	• The percentage of patients who require supplemental oxygen.
	• Change from baseline based on the daily collection of the WHO Clinical Progression Scale.
Statistical Methods	General Considerations:
	In general, continuous data will be summarized by descriptive statistics, including number of patients, mean, standard deviation, median, minimum, and maximum. Categorical data will be summarized by the number and percentage of patients. Safety:
	Safety assessments will include AEs, clinical laboratory tests, and vital signs. All safety data will be summarized for the safety population using descriptive statistics. Pharmacodynamics :
	The fold change from baseline at each evaluation time and the maximum fold change of absolute lymphocyte counts achieved will be summarized by treatment (bempegaldesleukin/SOC or placebo/SOC).
	Disease Measurement:
	Disease measurement will be summarized by treatment group for the safety population using descriptive statistics.

Protocol No. 20-214-34

[figure not shown]

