3.0 STUDY OBJECTIVES

3.1 **Primary Objectives**

The primary objectives are:

- To evaluate the safety, tolerability, pharmacokinetics, and pharmacodynamics of bempegaldesleukin/SOC compared with placebo/SOC in patients with mild COVID-19.
- To evaluate the safety and tolerability of bempegaldesleukin administered as single IV dose and to define the RP2D of bempegaldesleukin in patients with mild COVID-19.
- To assess the effect of bempegaldesleukin on the time course and extent of changes in absolute lymphocyte counts.

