9.0 STATISTICAL PLAN

9.1 General Considerations

In general, continuous data will be summarized by descriptive statistics, including number of patients, mean, standard deviation, median, minimum, and maximum. Categorical data will be summarized by the number and percentage of patients. Unless otherwise specified, data will be summarized by treatment arm.

All disease measurement endpoints will be analyzed using all the patients who are enrolled. All safety endpoints will be summarized using the Safety population.

A detailed description of analysis methods will be provided in the statistical analysis plan (SAP).

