9.7.1 Pharmacodynamics

The fold change from baseline at each evaluation time and the maximum fold change of absolute lymphocyte counts will be summarized descriptively by treatment group and a data listing will be provided. Changes to these pharmacodynamic endpoints may be made in the SAP prior to database lock and unblinding of patient treatment assignment.

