5.0 GENERAL ANALYSIS CONSIDERATIONS

The statistical analyses will be reported using summary tables and data listings. Continuous variables will be summarized with means, standard deviations, medians, minimums, and maximums. Categorical variables will be summarized by counts and by percentage of patients in

corresponding categories. All summary tables will be presented by treatment. For patients who receive placebo, the data will be pooled as one placebo group.

Individual subject data obtained from the case report forms (CRFs) and any derived data will be presented by subject in data listings. Data listings will be sorted by the treatment group, subject, visit date, and time, if applicable.

All analyses and tabulations will be performed using SAS Version 9.4 or higher. All outputs will be presented in rich text format (RTF).

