6.0 ANALYSIS POPULATIONS

Screened patients: All patients who signed study participation informed consent.

Enrolled patients: All patients who are assigned/randomized to either the bempegaldesleukin/SOC or placebo/SOC treatment groups.

Safety/Treated Population: All patients who receive at least 1 dose (full or partial dose) of study drug.

Pharmacokinetic Population: All patients in the Safety Population with at least one measurable concentration.

Immunogenicity Population: All patients in the Treated Population with at least baseline and one post-baseline ADA assessment.

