12.0 CHANGES TO PROTOCOL-SPECIFIED ANALYSES

No changes from the protocol-specified analyses are planned.

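### The primary lymphocyte endpoint has no stated estimate against placebo, and the plan is inconsistent on whether it is tabulated by dose level

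*Protocol*

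**What the plan says.** Protocol Section 3.1 makes the time course and extent of ALC change a primary objective. It also sets pharmacodynamics as a comparison: "bempegaldesleukin/SOC compared with placebo/SOC in patients with mild COVID-19". Section 5.3 lets the Cohort Review Committee (CRC) use lymphocyte effects as one possible input to the RP2D.

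The planned analysis is brief:

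- **Synopsis, Statistical Methods:** fold change at each time is summarized, and the "maximum fold change of absolute lymphocyte counts achieved will be summarized by treatment (bempegaldesleukin/SOC or placebo/SOC"). Two treatments are named and no dose level.
- **Protocol 9.7.1:** fold change and maximum fold change of "absolute lymphocyte counts will be summarized descriptively by treatment group and a data listing will be provided". The section allows the SAP to alter these endpoints before database lock and unblinding.
- **Protocol 9.1:** "Unless otherwise specified, data will be summarized by treatment arm". The general statistics for continuous data are n, mean, SD, median, minimum and maximum.
- **SAP 5.0:** tables are by treatment. Pooling is stated for placebo only: "For patients who receive placebo, the data will be pooled as one placebo group".
- **SAP 6.0:** enrolled patients are those "assigned/randomized to either the bempegaldesleukin/SOC or placebo/SOC treatment groups".
- **SAP 12.0:** "No changes from the protocol-specified analyses are planned".

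Only Protocol 2.2.4.3 gives a window for the maximum (Day 6 to Day 8). The synopsis and 9.7.1 give none.

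**The concern.** There are two gaps.

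First, the columns of the lymphocyte tables are not defined. If they follow the two treatments in the synopsis, three doses spanning a fourfold range share one column. The table then cannot show the dose separation that a lymphocyte-based RP2D argument would rest on.

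Second, the objective is comparative but the plan names no comparative quantity. Two columns of fold changes leave the reader to judge the difference by eye, with no interval, in groups of 5 active patients. This matters most for the maximum, which tends to exceed 1 in untreated patients simply because it picks the highest of several noisy counts. The predose count enters only as a divisor, so a chance baseline imbalance in a group of 5 can carry into the result.

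**Working it through.** **The plan's own figures.** There is no powered hypothesis to reproduce. Planned size: 3 cohorts × 10 = 30, as stated. The predicted fold changes in Table 3 are maximum over baseline: 1.95/1.10 = 1.77, 2.44/1.11 = 2.20, 2.89/1.11 = 2.60, all as stated. Section 2.2.4.3 adds 1.32 at 0.00075 mg/kg and 1.49 at 0.0015 mg/kg.

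**If the active doses shared one column.** Geometric mean: (1.32 × 1.49 × 1.77)^(1/3) = 1.52. Arithmetic mean: 4.58/3 = 1.53. The hidden top-to-bottom ratio is 1.77/1.32 = 1.34.

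**Do the documents pool them?** The synopsis points towards two columns, and SAP 6.0 uses the same two names, although there it defines a population. Three places point the other way:

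- SAP 5.0 singles out placebo for pooling, which would be odd if the active cohorts were pooled too.
- SAP 9.0 summarizes PK parameters for each treatment group and gives an additional total only for Tmax, CL, half-life and Vz, not for Cmax or AUC. That split makes sense if a treatment group is a dose level.
- SAP 11.1 speaks of active treatment groups in the plural, by dose level.

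The term therefore has two readings, and neither is fixed for the lymphocyte tables.

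**The maximum with no drug effect.** Hematology is drawn predose and on Days 2, 3, 4, 6 and 8 (Section 1.2). Assume independent normal errors on the log scale with within-patient SD s, and no true change. The expected maximum of five standard normals is about 1.16, so the typical maximum fold change is about exp(1.16 s). Simulated medians for s = 0.10, 0.15 and 0.20:

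- All five visits: 1.12, 1.19, 1.26.
- Days 6 and 8 only: 1.06, 1.09, 1.12.

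The upper end of the first row approaches the 1.32 predicted at the lowest dose. Taking the median over patients does not remove this shift. A ratio to placebo over the same window largely does.

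**Baseline adjustment.** Log-SDs from the 5th and 95th percentiles in Table 3 at 0.003 mg/kg (simulated cancer patients), as ln(P95/P5)/3.29:

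- Baseline: s1 = ln(2.05/0.599)/3.29 = 0.374.
- Maximum: s2 = ln(4.20/0.976)/3.29 = 0.444.

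For a baseline-maximum correlation ρ (assumed), the variance of log fold change is s1² + s2² − 2ρ·s1·s2, and the baseline-adjusted variance is s2²(1 − ρ²). The ratio of the first to the second is 1.32 at ρ = 0.3, 1.16 at 0.5 and 1.04 at 0.7. It equals 1 at ρ = s1/s2 = 0.84 and is about 1.02 at 0.9.

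A one-standard-error baseline imbalance (5 versus 15) shifts log fold change by |ρ·s2/s1 − 1| × s1 × √(1/5 + 1/15). This is 0.12 at ρ = 0.3, 0.03 at 0.7 and 0.01 at 0.9, against a predicted ln 1.32 = 0.28.

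**What a by-dose contrast would deliver.** Each dose (5) against pooled placebo (15), with 26 df and t = 2.056: the 95% CI factor is exp(2.056 × SD × √(1/5 + 1/15)). At an assumed SD of 0.35 this is exp(0.372) = 1.45. If the predictions hold and placebo does not change:

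| Assumed log-SD | 0.00075 mg/kg | 0.0015 mg/kg | 0.003 mg/kg |
|---|---|---|---|
| 0.2 | 1.32 (1.07–1.63) | 1.49 (1.21–1.84) | 1.77 (1.43–2.19) |
| 0.3 | 1.32 (0.96–1.81) | 1.49 (1.08–2.05) | 1.77 (1.29–2.43) |
| 0.4 | 1.32 (0.86–2.02) | 1.49 (0.97–2.28) | 1.77 (1.16–2.71) |

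The predicted trend per dose doubling is exp[(ln 1.77 − ln 1.32)/2] = 1.16, with power of about 61%, 32% and 20% at SD 0.2, 0.3 and 0.4.

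**The case against.** The strongest reply is that no passage says the active doses are pooled. That is correct. A reader might infer from the synopsis parenthetical that pooling was decided, but SAP 5.0, 9.0 and 11.1 point against it. What stands is that the wording conflicts and should be settled.

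A reader might also infer that the plan cannot yield dose-response information. The documents do not support that. A patient-level lymphocyte listing is planned (9.7.1), and the CRC reviews available pharmacodynamic data as each cohort ends (5.3). The RP2D rests on the totality of data, with lymphocytes an optional input. By-dose results can be produced; they are just not specified.

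The upward skew of raw ratios is a further tempting charge. It touches only the mean. Medians are planned too, and the protocol's predictions are themselves medians.

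The SAP's numbering runs from 7.6.4 to 9.0, so a section covering this endpoint may exist but not be visible. Its absence is not counted here. SAP 12.0 does not settle what such a section would say, because the SAP does depart from the protocol elsewhere: mean change on the WHO scale in Protocol 9.6 becomes shift categories in SAP 7.6.2. The finding therefore rests on the protocol text and the visible SAP.

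Finally, descriptive analysis is normal in a Phase 1b study without a sample size calculation, and a model will not rescue precision. At log-SD 0.35, top versus bottom dose (5 versus 5) has a CI factor of exp(2.056 × 0.35 × √(2/5)) = 1.58, wider than the 1.34 ratio of interest. This stands, and it is why the request is for estimation and not for a test.

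**Conclusion.** The concern holds in a limited form and is worth acting on. For a primary objective framed against placebo, the visible plan gives descriptive fold changes only, with no placebo-referenced estimate, interval or baseline adjustment. It also leaves unclear whether the columns are doses or arms.

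If the columns are arms, predicted effects differing 1.34-fold appear as one value near 1.52. If the maximum is read without reference to placebo, about 1.12 to 1.26 of apparent fold change needs no drug effect. That range assumes independent errors, within-patient log-SD of 0.10 to 0.20, and all five visits in the window.

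The benefit of baseline adjustment is less certain. Unadjusted log fold change carries about 32% more variance at a correlation of 0.3, 4% at 0.7 and essentially none at 0.84. The correlation is assumed, and the SDs come from simulated cancer patients, not mild COVID-19. The case for the change rests mainly on the placebo contrast and the dose-level columns.

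**What to change.** 1. In the synopsis, Protocol 9.7.1 and the SAP, state that every lymphocyte table is by bempegaldesleukin dose level plus one pooled placebo group.
2. State the window for the maximum: either adopt the Day 6 to Day 8 window of Protocol 2.2.4.3, or name another and say why.
3. Add one model with log maximum ALC in that window as response, and log predose ALC and dose level (pooled placebo as reference) as terms. Report each dose's geometric mean ratio to placebo with a 95% CI, labelled as estimation.
4. Keep the descriptive fold changes beside it. A dose trend may be shown, with a note that it will be imprecise.

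The cost is SAP wording and one extra model on data already collected, and Protocol 9.7.1 permits the change before lock and unblinding. The drawback is visibly wide intervals, which show the CRC how much the lymphocyte data can say about dose.
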